2.1. Hypotheses

Our hypothesis is that peanut immunotherapy will induce changes in subject's cellular and humoral immune system and thus make them less allergic to peanut allergens.

2.2. Primary Objective(s) of the overall research program

Determine whether peanut oral immunotherapy induces clinical tolerance as assessed after the initial 3 month peanut avoidance period

2.3. Secondary Objective(s) of the overall research program

• Identify the basic immune mechanisms which can explain the differences in the effects of OIT in desensitized vs. tolerant individuals.

• Determine whether immune monitoring measurements reflecting underlying mechanisms during OIT can be used to predict responses to OIT in individual subjects and, ultimately, to improve the safety and efficacy outcomes in peanut OIT protocols.

Figure 1: Study Design Part II: Randomization for Arm A,B,C* Sub-study GI Endoscopy -Baseline Peanut OIT (arms A and B)* Placebo (arm C)* (N=95) (N=25) Part III: Initial Dose Escalation Day Part III: Build up phase with every 2 Week Visits Dosing to 4g peanut protein maximum daily Sub-study GI Endoscopy Week 52 Part IV: Maintenance Every 13wk Visits (approximately Wks52—104) Dosing at 4g peanut protein daily. First on-study DBPCFC at 104wks. Then at week 104, do subjects meet criteria: 1) on OIT treatment for minimum 104 weeks, 2) taking daily maintenance dose of 4,000 mg protein for at least 13 weeks, 3) no severe reactions (Grade 3, Appendix 4 to home dosing from Week 92-Week 104, and/or 4) no reactions. (objective. Appendix 4) at the Week 104 DBPCFC? Sub-study GI Endoscopy YES Week 104 Part V: Tolerance and Desensitization testing phase every 13wk **Desensitization Failure** Visits (Wks117-156) Sub Study GI Endoscopy Week 117 At DBPCFC every 13wk visit, is there clinical reactivity on DBPCFC? If Arm B, Desensitization Failure YES NO, then continue part V If Arm A, Tolerance Failure

* The 120 enrolled subjects will be randomized 2.4:1.4:1 (please see section 13). Thus, there will be three arms: (1) Arm A on peanut OIT until week 104 and once meeting criteria [*i.e. 1*) on OIT treatment for minimum 104 weeks, 2) taking daily maintenance dose of 4,000 mg protein for at least 13 weeks, 3) no severe reactions (Grade 3, APPENDIX 4) to home dosing from Week 92-Week 104, and/or 4) no objective reactions, (Appendix 4) at the Week 104 DBPCFC] has been assigned to avoid peanut (i.e. 600 mg oat flour). (2) Arm B on peanut OIT until week 104 and once meeting criteria, has been assigned to be maintained on 300 mg peanut protein (i.e. 600 mg oat flour). (3) Arm C that is maintained on placebo (oat flour) and once meeting criteria, this arm will receive 600 mg oat flour beginning on week 104. This will be true even if a subject in the placebo group meets criteria at week 104. This way all participants will receive approximately the same volume of flour so that the subject blinding will be easier to maintain. The decision to maintain subjects on only 300 mg peanut protein after week 104 is for ease of eating peanut and to test if a lower amount of protein can still maintain desensitization.

3. Study Design

3.1. Description of Study Design

A Phase 2, single-center, randomized double blind, placebo controlled study of the induction of peanut tolerance by oral immunotherapy (OIT). Our intent to treat population will be 120 subjects, ages 7-55 years, with an allergy to peanut, as determined by DBPCFC, history, clinical symptoms, and positive skin prick test (SPT). Please see Figure 1.

First, subjects will be screened (Part I, Figure 1). The 120 enrolled subjects will be randomized 2.4:1.4:1 (please see section 13). Thus, there will be three arms: (1) Arm A on peanut OIT until week 104 and once meeting criteria *[i.e. 1) on OIT treatment for minimum 104 weeks, 2) taking daily maintenance dose of 4,000 mg protein for at least 13 weeks, 3) no severe reactions (Grade 3, APPENDIX 4) to home dosing from Week 92-Week 104, and/or 4) no objective reactions, (Appendix 4) at the Week 104 DBPCFC]* has been assigned to avoid peanut (i.e. 600 mg oat flour). (2) Arm B on peanut OIT until week 104 and once meeting criteria, has been assigned to be maintained on 300 mg peanut protein (i.e. 600 mg oat flour). (3) Arm C that is maintained on placebo (oat flour) and once meeting criteria, will receive 600 mg oat flour beginning on week 104. This will be true even if a subject in the placebo group meets criteria at week 104. This way all participants will receive approximately the same volume of flour so that the subject blinding will be easier to maintain. The decision to maintain subjects on only 300 mg peanut protein after week 104 is for ease of eating peanut and to test if a lower amount of protein can still maintain desensitization. This upfront randomization is performed because our statistical analysis plan is focused on an intent to treat analysis.

All arms will undergo an Initial Dose Escalation (IDE) Day and updosing regimen with a maintenance phase of OIT or placebo to a maximum of 4,000 mg protein daily, as peanut flour, in the OIT groups, and to a maximum of an equivalent amount of oat flour for the placebo group). (Part III, Figure 1). After maintenance is achieved, all subjects will begin performing DBPCFCs (staged so as to ensure safety) at Week 104 and every 13 weeks thereafter (Part IV, Figure 1). At Week 104, individuals that reach criteria (Part IV, Figure 1) will, based on the randomization that was done at the start of the study, either stop therapy with peanut and be switched to oat flour, or will be maintained on 300 mg peanut protein per day (Parts V, Figure 1). If subjects fail the week 104 DBPCFC they will not be given home doses. Those that fail the week 104 FC will remain in the study and return for a study completion visit at week 117 to meet the primary endpoint (will be analyzed in the intent to treat comparisons). All subjects will be evaluated every 13 weeks thereafter until the end of study.

Individuals in Arm A will be defined as "clinically tolerant" if there is no clinical reactivity at the Week 104 and Week 117 (or equivalent) DBPCFC. Clinical reactivity is defined as any objective reaction based on the Bock's Criteria (**Appendix 4**). Individuals in Arm A who meet the definition of "clinically tolerant" will continue to avoid peanut protein (i.e. continue on 600 mg per day of oat flour) as long as each subsequent DBPCFC (performed every 13 weeks until end of study) shows no clinical reactivity.

Individuals in Arm B will be defined as "desensitized" to a minimum of 300 mg per day of peanut protein if they show no clinical reactivity at DBPCFCs (week 117 (or equivalent) to end of study).

Individuals in Arm C will be defined as "natural loss of responsiveness" if they show no clinical reactivity at DBPCFCs (week 117 (or equivalent) to end of study).

We plan to identify the basic immune mechanisms which can explain the differences in the effects of OIT in individuals who do or do not become clinically tolerant and to determine whether immune monitoring can predict the safety and efficacy outcomes in peanut OIT protocols. After initial screening and enrollment, there are three phases of the study:

- Dose escalation and Build up Phase (Part III, Figure 1)
- Maintenance phase (Part IV, Figure 1)
- Tolerance and Desensitization Testing phase (Part V, Figure 1)

Overall, 120 subjects who are eligible will undergo the Initial Dose Escalation Day. Subsequent updosing visits will occur every 2 weeks as a part of the build-up phase. They will continue to updose until they reach 4,000 mg protein daily, which is the maximum maintenance amount of protein. We expect active OIT treatment subjects to reach 4,000 mg of peanut protein between 44-78 weeks.

GI Sub Study.

Subjects will also have the opportunity to participate in this study via a separate consent after they have enrolled in the study and prior to starting IDED at week 0.

Treatment and Desensitization Failures:

A treatment failure will be defined as a) failure to reach 1.5 mg peanut protein (single dose) during the Initial Dose Escalation Day or b) failure to reach 1,000 mg peanut protein by week 104.

Subjects who do not meet the criteria (Part IV, Figure 1) at Week 104 and who demonstrate clinical reactivity (objective, Appendix 4) will be considered desensitization failures.

If Arm B subjects demonstrate clinical reactivity (objective, Appendix 4) in any DBPCFC from Week 117 (or equivalent) to end of study, they will be considered desensitization failures.

If Arm A subjects demonstrate clinical reactivity (objective, Appendix 4) in any DBPCFC from Week 117 (or equivalent) to end of study, they will be considered tolerance failures.

Research staff may be unblinded when the primary endpoint (at the completion of the week 117 visit) is reached for the study. Treatment failures, desensitization failures, and tolerance failures may be unblinded (both participant and research staff) at week 117 and/or may be followed until the end of the study at the specified study visits (Appendix 1, Schedule of Events, early completion visit). They will be considered in statistical analyses of the intent-to-treat population.

Integration with mechanistic science program: We will use blood samples and clinical outcome measurements from this study to identify specific features of the immune response that are associated with "clinical tolerance" at week 104, 117 (or equivalent), 130, 143, and 156. We will also determine special immune features associated with subjects who are desensitized at week 104, 117 (or equivalent), 130, 143, and 156. It will be important to compare any of the immune features to those of the placebo arm, treatment failures, and desensitization failures. Treatment groups A, B, and C are key cohorts to be able to identify possible quantitative and/or qualitative differences in immune phenotypic features among subjects in the tolerance, desensitization, and placebo groups, since such information is critical to our efforts to identify possible differences in the mechanisms that underlie immune tolerance vs. desensitization.

Study Design Safety Considerations

The design considers important safety issues:

- All updosing visits will be supervised in a hospital setting where trained study physicians are available within 60 seconds
- Standing orders from an MD are provided for all clinical study personnel (RN, NP, PA, etc.) to initiate treatment of reactions immediately (i.e., prior to MD notification), including IM administration of epinephrine, based on their own clinical judgment.
- A crash cart with pediatric and adult equipment is available in close proximity (within 50 feet) of all patient hospital rooms
- A code team is available for pediatric and adult patients
- The peanut OIT will only escalate to a maximum 6 mg single dose during the initial dose escalation Day
- Dosing symptoms and adverse events will be captured throughout the study
- Subjects will be prescribed an epinephrine auto-injector (if not prescribed by a treating clinician previous to study entry) and all subjects will be trained in its use

Subjects will be cautioned against consuming any peanuts or peanut-containing foods other than study-supplied food allergen while on study.

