6.1.2. Placebo (Oat Flour)

The placebo, oat flour, will be purchased commercially from the following manufacturer:

Arrowhead Mills, Inc.

A Division of the Hain Celestial Group. Inc.

Melville, NY 11747

Toasted oat flour, prepared as described in IND **sectors** is acceptable based upon being approved and used previously for IND **sectors**.

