The subject's sensitivity to peanut allergen is defined as the dose at which the subject experiences allergic reactions. All symptoms and signs will be evaluated and rated based on a standardized oral food challenge scoring system (Appendix 4).

During the oral food challenge, there should be increased hydration (i.e. about 16 oz or more orally).

Updosing during the DBPCFC will be stopped when the Principal Investigator (or designee) finds symptoms and/or signs that indicate a definite allergic reaction (Bock scoring system (objective, **Appendix 4**) has occurred based on clinically significant changes in reported symptoms, physical findings, or vital signs that the subject is experiencing to the challenge material. The challenge will consist of 7 doses (peanut or placebo), given about every 15-30 minutes for lower doses and about every 45 minutes or longer for higher doses (in bold): 5 mg, 50 mg, 220 mg, **625 mg, 1,000 mg, and 1,050 mg and 1,050 mg** (4,000 mg protein total). The doses for DBPCFCs conducted on or after Week 104 in this
protocol were selected with the rationale that some study subjects will be receiving placebo and would be expected to maintain the same level of sensitivity displayed at the screening DBPCFC to a cumulative dose of 500 mg of peanut protein. Both peanut and oat protein will be concealed in a food that masks the taste. After the last dose of the DBPCFC, the subject will be monitored for 2 hours and then discharged home. Subjects will be considered to have tolerated the OFC if they do not experience any objective reactions by Bock's Criteria (**Appendix 4**).

If the subject experiences reactions, they will be treated with the necessary rescue medications. They will be observed for a minimum two hours after the final administered dose and discharged home only when deemed clinically stable by a study physician.

After the Week 104 DBPCFC, subjects who meet the following criteria will reduce their daily maintenance dose to 300 mg peanut protein daily or to discontinue peanut protein daily dosing entirely (i.e., switch to 600mg oat flour):

- On OIT treatment for minimum 104 weeks,
- Taking daily maintenance dose of 4,000 mg protein for at least 3 months,
- No severe reactions (Bock's Criteria Grade 3, APPENDIX 4) to home dosing from Week 92-Week 104, and/or
- No objective reactions by Bock's Criteria, Appendix 4 at the DBPCFC at Week 104

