Subjects who do not meet these criteria at Week 104 will be considered desensitization failures and will be offered a follow-up protocol that is separate from this protocol once they reach the primary endpoint. They will be considered in statistical analyses of the intent-to-treat population.

After Week 104, double blinding will continue by using the same quantity of flour for all groups (600 mg total of oat flour daily for placebo group and 600 mg total of oat flour daily for avoidance group; approximately 600 mg total of peanut flour --to provide exactly 300 mg peanut protein—for the 300 mg peanut protein group).

Separate GI Sub Study.

Subjects will undergo the second endoscopy at week 52, and a third endoscopy at week 104 and a fourth endoscopy at week 117 (or equivalent). These will be performed by a board certified gastroenterologist at Stanford Endoscopy suite. This will be performed under mild anesthesia using fentanyl, versed and midazolam and subjects will be observed in the endoscopy recovery room per standard of care. Biopsies will be taken from the esophagus, stomach and duodenum.

Weeks 117 (or equivalent), 130, 143, and 156 - On Study DBPCFC (to 4,000 mg)

At Weeks 117 (or equivalent), 130, 143, and 156, subjects will have a DBPCFC to 4,000 mg (as per staged challenge above) to assess tolerance. Subjects who fail these challenges (i.e., who exhibit objective reactions by Bock's Criteria, **Appendix 4**) will be offered a follow-up protocol that is separate from this protocol.

Subjects who are randomized either to 300 mg peanut protein or peanut avoidance or the placebo subjects who pass the week 104 criteria will return to CFRU at Weeks 117 (or equivalent), 130, 143, and 156. Each of these visits will include a physical assessment, spirometry, skin test, blood draw for mechanistic studies, and a DBPCFC to 4,000 mg as outlined above to assess clinical reactivity.

During the oral food challenge, there should be increased hydration (i.e. about 16 oz or more given orally).

There are no data indicating that repeating food challenges every 3 months will or will not induce desensitization or otherwise affect the outcomes in this study. Our preliminary studies in which we have performed DBPCFCs every 3 months in a separate phase 1 study cohort (n=87 subjects) have demonstrated no increased risk of sensitization.

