13.1 Overview

This double blind, randomized, placebo controlled study in peanut-allergic children and adults intends to identify basic immune mechanisms that explain the effects of OIT in individuals who do or do not become clinically tolerant and to determine whether immune monitoring can predict safety and outcomes in OIT protocols.

The 120 enrolled subjects will be randomized 2.4:1.4:1. Thus, there will be three arms: (1) Arm A (60 subjects) on peanut OIT until week 104 and once meeting criteria [*i.e.* 1) assigned to OIT treatment for minimum 104 weeks, 2) reaching maintenance 13 weeks prior to DBPCFC at week 104 3) no severe reactions (Grade 3, APPENDIX 4) to home dosing from Week 92-Week 104, and/or 4) no objective reactions, (Appendix 4) at the Week 104 DBPCFC] has been assigned to avoid peanut (i.e. 600 mg oat flour). (2) Arm B (35 subjects) on peanut OIT until week 104 and once meeting criteria, has been assigned to be maintained on 300 mg peanut protein (i.e. 600 mg peanut flour). (3) Arm C (25 subjects) that is maintained on placebo (oat flour) and once meeting criteria, will receive 600 mg oat flour beginning on week 104. This will be true even if a subject in the placebo group meets criteria at week 104. This way all participants will receive approximately the same volume of flour so that the subject blinding will be easier to maintain. The decision to maintain subjects on only 300 mg peanut protein after week 104 is for ease of eating peanut for so long. This upfront randomization is performed because our statistical analysis plan is focused on intent-to-treat principles.

The primary analysis is an intent-to-treat comparison of success rates between arms A and C, where success is defined by reaching and passing the DBPCFC at both 104 weeks and 117 (or equivalent) weeks.

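### Section 3.1 and the Figure 1 footnote gloss Arm B's 300 mg peanut protein after Week 104 as oat flour, contradicting themselves and the rest of the protocol

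*Protocol*

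**What the plan says.** In Section 3.1 of the protocol, Arm B is described after Week 104 as follows: "has been assigned to be maintained on 300 mg peanut protein (i.e. 600 mg oat flour"). The footnote to Figure 1 uses the same words. In that description Arm A "has been assigned to avoid peanut (i.e. 600 mg oat flour"), and Arm C "will receive 600 mg oat flour beginning on week 104".

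Section 13.1 describes Arm B differently: "has been assigned to be maintained on 300 mg peanut protein (i.e. 600 mg peanut flour"). The synopsis agrees with Section 13.1 in both its Study Design and Treatment Description rows. Section 8.3, in explaining how the blind is kept after Week 104, assigns oat flour to the placebo and avoidance groups and "approximately 600 mg total of peanut flour" to the 300 mg peanut protein group.

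Two further sentences bear on the meaning of oat flour in this phase. Later in Section 3.1, subjects who meet the Week 104 criteria will "either stop therapy with peanut and be switched to oat flour, or will be maintained on 300 mg peanut protein per day". Section 8.3 offers, as the alternative to 300 mg daily, "to discontinue peanut protein daily dosing entirely (i.e., switch to 600mg oat flour"). Section 6.1.2 fixes the role of the material: "The placebo, oat flour, will be purchased commercially".

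**The concern.** The three arms are defined by what they take, and Arms A and B are meant to differ only after Week 104. A protocol that names two materials for Arm B in that phase leaves the defining feature of the arm in conflict. The conflict is in the section headed as the description of the design and in the note to the design figure, where a reader would look first.

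Several analyses need Arms A and B to receive different products after Week 104:

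- the A versus B comparison of success rates (Sections 13.4.3 and 13.6);
- the Section 3.1 definition of an Arm B subject as desensitized;
- the secondary endpoint that compares the placebo, avoidance and 300 mg groups (Section 13.2);
- the mechanistic contrast between tolerance and desensitization (Section 3.1).

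If the oat flour gloss were acted on, none of these would measure what it is said to measure. The blind would also make such an error hard to notice: under Section 6.1.1.1 the cup label reads the same for peanut and placebo.

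**Working it through.** The main check is textual. These are all the places that name Arm B's material after Week 104, or that say what oat flour means in that phase.

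| Place in the protocol | Arm B material, or meaning of oat flour |
|---|---|
| Section 3.1, arm description | 300 mg peanut protein, glossed as 600 mg oat flour |
| Figure 1 footnote | 300 mg peanut protein, glossed as 600 mg oat flour |
| Synopsis, Study Design | 300 mg peanut protein, glossed as 600 mg peanut flour |
| Synopsis, Treatment Description | 300 mg peanut protein, glossed as 600 mg peanut flour |
| Section 13.1 | 300 mg peanut protein, glossed as 600 mg peanut flour |
| Section 8.3, blinding text | about 600 mg peanut flour |
| Section 3.1, later text | oat flour is the alternative to 300 mg peanut protein |
| Section 8.3, Week 104 criteria | the switch to 600 mg oat flour means stopping peanut protein |
| Section 6.1.2 | oat flour is the placebo |

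**Step 1: within the sentence.** The main clause gives Arm B peanut protein and the parenthesis equates that with oat flour. The protocol uses oat flour as placebo and equates switching to it with stopping peanut protein. Both halves of the sentence cannot hold.

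**Step 2: across sections.** Two places say oat flour and four say peanut flour. The same faulty words stand intact in two separate places, so this is not damage from text extraction or redaction.

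**Step 3: against the protocol's own product figures.** The sample certificate of analysis for the peanut flour gives protein of 51% (N x 5.46) or 58% (N x 6.25). Then 600 mg x 0.51 = 306 mg and 600 mg x 0.58 = 348 mg. The peanut flour gloss is therefore close to 300 mg protein on the 51% figure. No figure in the protocol would let 600 mg of oat flour supply 300 mg of peanut protein. This locates the contradiction; the choice of product remains the sponsor's.

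**Step 4: how many subjects.** Section 13.1 allots 60, 35 and 25 subjects to Arms A, B and C. Arm B is 35/120 = 29%. This is a ceiling. Only subjects who meet the Week 104 criteria move to the later product, and Section 3.1 says that those who fail the Week 104 challenge receive no home doses.

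**Step 5: is the primary comparison touched?** Section 13.7 states 90% power for A (n = 60, rate 0.35) versus C (n = 25, rate 0.05), two-sided alpha 0.05. With the pooled normal formula:

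- pooled rate = (60 x 0.35 + 25 x 0.05)/85 = 22.25/85 = 0.2618
- standard error under the null = sqrt(0.2618 x 0.7382 x (1/60 + 1/25)) = 0.1046
- standard error under the alternative = sqrt(0.35 x 0.65/60 + 0.05 x 0.95/25) = 0.0754
- z = (0.30 - 1.96 x 0.1046)/0.0754 = 1.26, so power is 89.6%

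Exact enumeration gives 91.5% for the pooled z test and 89.2% for Fisher's exact test. The stated 90% is reproduced. Arm B enters none of these inputs, so the primary comparison does not depend on this point.

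**The case against.** The strongest reply is that nobody reading the protocol as a whole would be misled. The faulty sentence still says that Arm B stays on 300 mg peanut protein. The same paragraph explains that the lower amount is there to test whether desensitization can be maintained. Section 3.1 later sets oat flour against 300 mg peanut protein, and Section 8.3, the operational text, lists the flour group by group. Most of this stands. It makes a copying slip the likely explanation and keeps the intended contrast between Arms A and B visible. It does not remove the contradiction from the controlling description of the design.

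Three stronger readings are tempting, and the document supports none of them.

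- A reader might infer that Section 3.1 makes Arms A and B identical after Week 104, so that the expected A versus B difference is zero. The sentence contradicts itself; it does not order placebo for Arm B. Identical arms would follow only if the gloss were followed and the main clause ignored.
- A reader might infer that product has been, or will be, wrongly dispensed. Section 6.1.1.2 describes batch records for each dose and Section 3.5.2 places the randomization lists with unblinded pharmacists. The batch records are not shown, and nothing indicates that cups are filled from the parenthesis in Section 3.1.
- A reader might infer a safety problem at challenge or on accidental exposure. On-study challenges start at 5 mg for every arm, and Section 8.3 gives the reason that some subjects will be on placebo and are expected to have kept their sensitivity. Subjects are also told to avoid dietary peanut and to keep their usual vigilance. The challenge design already allows for subjects who are not taking peanut.

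**Conclusion.** The point holds as an internal contradiction about the product of one randomized arm. It is wrong as written in two places, Section 3.1 and the Figure 1 footnote, and is probably a copying slip. It deserves correction because it stands in the main design text and because the A versus B comparison and the Arm B definition of desensitization depend on that product.

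Its reach is limited. At most 35 of 120 subjects are concerned, fewer once the Week 104 criteria are applied. The comparison at risk is secondary and has no stated power. Any loss of meaning is conditional on the oat flour gloss being followed, which the protocol does not show. The primary analysis and its 90% power stand. The conclusion rests on the protocol text alone, without sight of the pharmacy or batch-record instructions.

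**What to change.** The sponsor should reconcile the arm description in Section 3.1 and the Figure 1 footnote with the synopsis (both rows), the later text of Section 3.1, Section 8.3 (both the criteria and the blinding text) and Section 13.1. Arm B's product after Week 104 should then be stated in the same words everywhere. The pharmacy and batch-record instructions should be checked against the reconciled text. Which product or dose is correct is for the sponsor to state and is not proposed here.

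The cost is small: a short wording change wherever the sponsor finds the text to be in error, one check of dispensing documents, and the IRB approval that Section 16.1 requires for any amendment. No sample size, endpoint or analysis changes.
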